#### **SCOFF**

The Hungarian version (Dukay-Szabó et al. 2016) of the SCOFF screening test (Morgan et al. 2000) will be used to measure non-disorder-specific risk level for eating disorders. At least two positive answers (score of 2) will indicate a high likelihood of an eating disorder (Dukay-Szabó et al. 2016).

Ad hoc items to assess addiction severity

In the absence of a concise and validated, broad-focus screening tool to assess the severity of both substance-related and behavioral addiction problems, a 4-item ad hoc tool will be created for the purposes of the present study. One question each will refer to the past-month frequency of substance use and excessive behaviors, while further two questions will explore the extent to which participants perceive that their substance use or excessive behaviors cause problems in their lives.

Meaning in Life Questionnaire (MLQ)

The Hungarian version (Martos & Konkolÿ Thege 2012) of the MLQ (Steger et al. 2006) will be used to assess both the presence of and search for meaning in a respondent's life as eudaimonic wellbeing indicators. While the former is an indicator of positive mental health, the latter is typically considered as an indicator of ill mental health and therefore, higher scores indicate less favorable mental status. The scale consists of 10 items (5 items measuring both subconstructs).

WHO Well-being Index (WBI-5)

The Hungarian (Susánszky et al. 2006), 5-item version of the WHO Well-being Index (Bech et al. 1996) will be used to measure participants' overall subjective well-being as a hedonic indicator of wellbeing.

#### II. STATISTICAL ANALYSIS PLAN

All analyses will be carried out using SPSS for Windows. Baseline characteristics of study completers versus drop-outs will be compared using the Mann-Whitney U (age) and the chi-squared (categorical variables) test. Effect size will be expressed using effect size r (Mann-Whitney U test) and Cramer's V (Chi-squared test). Considering the likely non-normal distribution and occasionally ordinal nature (SCOFF) of the outcome variables, the effectiveness of the intervention will be investigated using Wilcoxon paired sample tests in the primary analyses. Separate comparisons will be made to explore potential changes from baseline to 4-week post-intervention as well as baseline to 6-month follow-up. Effect size r will be computed to express the magnitude of the changes.

Given that the normality assumption is relatively rarely examined and therefore parametric tests are used most often in effectiveness research, to facilitate inter-study comparability, repeated measures ANOVAs will be conducted as secondary analyses to investigate the main effect of time considering all three assessment points. For similar reasons, means and standard deviations (instead of medians and interquartile ranges) will be reported as descriptive data to allow easier comparisons across studies. A further set of ANOVAs will be run to investigate therapist effects. In these secondary analyses, effect size will be expressed by eta squared.

The Reliable Change Index (RCI) will be used to examine the clinical significance of changes on the individual level. Given the uncontrolled nature of the current study's design, a metric will be chosen that considers the tendency of regression to the mean, a threat to the validity of effectiveness studies without a control group. For this reason, the Edwards–Nunnally method will be used to examine the reliability of changes over time (Bauer et al. 2004).

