explanation of these processes use the morphic / morphogenic field and -resonance concepts (cf. storage) of the biologist Rupert Sheldrake (Sheldrake, 2011) in combination with the function of mirror neurons (cf. way of accessing stored information by non-members of the system) (Lahore, 2009).

Regardless of whether we fully understand the exact mechanisms of action of a therapeutic modality and if its certain assumptions fit the contemporary paradigms of health sciences, we argue that collecting empirical data on an intervention's effectiveness and safety is a public health necessity, especially if it is so widely used as family constellation therapy is (and it certainly could provide further impetus to the study of the mechanisms of action and the potential reconsideration of the accuracy of our paradigms).

The very limited number of previous prospective, peer-reviewed studies into family constellation therapy's therapeutic effectiveness reported that the intervention was effective in reducing general, non-diagnosis-specific psychopathology and psychological distress (Hunger et al., 2015; Krüger & Schmidt-Michel, 2003; Weinhold et al., 2013) as well as improving quality of life and functioning in interpersonal relationships (Hunger et al., 2014; Hunger et al., 2015).

The aim of the present study was to collect and analyze further data from the real life setting on family constellation therapy's effectiveness in improving mental health and its tolerability 1) using a mid-term time frame (≥6 months) to evaluate client outcomes, 2) employing active monitoring (not just passive surveillance) of potential iatrogenic effects, and 3) providing information on the presence or absence of therapist effects.

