## Participants and procedure

Participants of the study will be recruited in Hungary from individuals in the general population who will express their intent to participate in a 2-day family constellation workshop on a fee-for-service basis (private setting) with one of the three professionals participating in the study. All three intervention providers will be highly trained in both general mental health care delivery (one therapist with a background in clinical psychology, while the other two will be trained in medicine) and family constellation therapy (10-20 years of experience). Participation in the study will be voluntary and will occur as a combination of online and paper-pencil data collection after participants give their informed, written consent. Neither the therapists nor the participants will receive financial compensation for their participation.

The assessment protocol will include a pre-intervention assessment, a follow-up approximately 4 weeks after the intervention (this time is estimated to be necessary for the single-occasion, 2-day workshop to have most of its effects; cf. the focus on changes in perceived quality of interpersonal relationships and related mental health symptoms), and finally, six months post-intervention. Significant efforts will be made (follow-up email and three attempted phone calls) to encourage participants to complete the questionnaires at both follow-up assessment points.

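### The planned analyses use only people with follow-up scores, and the drop-out check does not name the outcome scales, so outcome-related loss could bias the 6-month change in either direction and go largely unseen

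*Combined protocol and SAP*

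**What the plan says.** The Statistical Analysis Plan states that "the effectiveness of the intervention will be investigated using Wilcoxon paired sample tests in the primary analyses", with separate comparisons of baseline against 4 weeks and baseline against 6 months. It adds that "repeated measures ANOVAs will be conducted as secondary analyses to investigate the main effect of time considering all three assessment points", and that "The Reliable Change Index (RCI) will be used to examine the clinical significance of changes on the individual level".

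On loss to follow-up it says only this: "Baseline characteristics of study completers versus drop-outs will be compared using the Mann-Whitney U (age) and the chi-squared (categorical variables) test". Effect size r and Cramer's V accompany those tests. No imputation, likelihood-based model, weighting or sensitivity analysis is named, and 'completer' is not defined although there are two follow-ups.

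Under Participants and procedure, the assessments are a baseline, "a follow-up approximately 4 weeks after the intervention", "and finally, six months post-intervention". An email reminder and three call attempts are planned at both follow-ups. Under Background and aims, the first listed feature of the study is "using a mid-term time frame (≥6 months) to evaluate client outcomes".

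**The concern.** A Wilcoxon pair and a reliable-change classification each need a baseline and a follow-up score. Standard repeated measures ANOVA needs all three scores. So each result describes people who stayed, and the different analyses may rest on different people. The share with reliable change is likewise a share of those with scores, not of those enrolled.

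If the people who stay differ in outcome from those who leave, the estimated change shifts. The SAP itself writes "Given the uncontrolled nature of the current study's design" when it deals with regression to the mean. The same feature means that no comparison group shares the selection and offsets it. Losing people who had not improved by 4 weeks makes the 6-month change look larger. Losing people with worse baseline scores makes it look smaller.

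The drop-out check is unlikely to reveal either pattern. It ties the Mann-Whitney test to age and otherwise covers categorical variables. It does not name baseline scores on the outcome scales (GSI, EXIS.pers, PHQ-15, MLQ, WBI-5, the addiction items), or the 4-week change of people lost by 6 months.

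**Working it through.** **Inputs.** The documents give no sample size, attrition rate, SD, correlation or expected change, so there is no figure of the plan to reproduce. Everything numerical here is assumed: scores Y1, Y2, Y3 (baseline, 4 weeks, 6 months) are jointly normal with SD 1, lower is better, and means are 0, -0.25, -0.25. Loss occurs at 6 months only, with log-odds rising by b per SD of a driver.

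**Step 1: bias in completers.** For normal scores,

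E[Y3 - Y1 | retained] = -0.25 + s × m,

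where m is the mean of the standardised driver among those retained and s = Cov(Y3 - Y1, driver) / SD(driver).

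Values of s by driver:
- worse baseline: r13 - 1
- poor 4-week change: (1 - r12 - r13 + r23) / √(2 - 2·r12)
- worse 4-week level: r23 - r12
- poor 6-month change: √(2 - 2·r13)

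Numerical integration gives m = -0.096 (20% loss, b = 0.5), -0.173 (20%, 1.0), -0.189 (40%, 0.5) and -0.332 (40%, 1.0).

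Two examples with r12/r23/r13 = 0.6/0.8/0.6, 40% loss and b = 1.0:
- 4-week change: s = 0.6/√0.8 = 0.671, so -0.25 + 0.671 × (-0.332) = -0.473.
- Baseline: s = -0.4, so -0.25 + (-0.4) × (-0.332) = -0.117.

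Completers' 6-month change, range over the four cells (true value -0.25):

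| Driver of loss | 0.7/0.7/0.7 | 0.8/0.6/0.6 | 0.6/0.8/0.6 |
|---|---|---|---|
| Worse baseline | -0.221 to -0.150 | -0.212 to -0.117 | -0.212 to -0.117 |
| Poor 4-week change | -0.287 to -0.379 | -0.280 to -0.355 | -0.315 to -0.473 |
| Worse 4-week level | -0.250 | -0.231 to -0.184 | -0.269 to -0.316 |
| Poor 6-month change | -0.324 to -0.507 | -0.336 to -0.547 | -0.336 to -0.547 |

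If b is counted per SD of the score instead of per SD of the change, the weakest 4-week-change case is -0.270. This gives the overall range of about -0.27 to -0.47 for that driver. Loss by 4-week level does no harm only if r12 = r23. That cannot be presumed when the first interval is about 4 weeks and the second about 5 months.

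**Step 2: low loss.** With 5-10% loss and b = 0.25-0.5, m runs from -0.0125 to -0.0488. The largest error is 0.894 × 0.0488 / 0.25 = 17.5% (6-month-change driver). The smallest non-zero error is 0.2 × 0.0125 / 0.25 = 1.0%. Hence roughly 1-18%, depending on the driver.

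**Step 3: what a likelihood model recovers.** With complete 4-week scores it returns about -0.25 for every baseline and 4-week driver. When unseen 6-month change drives loss it removes only 22-57% of the bias. For example, at equal correlations with 40% loss and b = 1.0, it moves -0.507 to -0.440, and 0.067/0.257 = 26%.

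**Step 4: detection.** Simulated with 100-200 enrolled, two-sided 0.05, the four cells above, and age correlated 0.1-0.3 with baseline score. When 4-week change drives loss, the age test is significant in 4-11% of runs, against 48-100% for a test on 4-week change. When baseline drives loss, the figures are 5-36% for age and 48-100% for a test on baseline score.

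**The case against.** **Retention may make this small.** The planned reminders and calls may keep loss low. That stands as far as it goes: at 5-10% loss with weak selection the error is modest. But these steps limit loss and do not analyse what is still missing, and the documents state no expected rate.

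**The check may be broader than it looks.** Loss that tracks age, sex, relationship status or education could show. So could loss that tracks the SCOFF cut-off, if SCOFF is entered as a category, though the SAP does not say it will be. This is fair, but the tests named leave no evident place for the continuous scales.

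**The primary test may barely move.** At a true change of -0.25 (correlation 0.7, 100-200 enrolled), Wilcoxon is significant in 88-100% of runs when poor 4-week change drives loss, against 87-100% without loss. So what shifts there is the size of the change, not the test result. This does not hold generally. With a true change of zero (150 enrolled, correlation 0.6, 10-40% loss, odds ratios 1.5-2.0), false-positive rates are 5-24% if 4-week change drives loss and 7-69% if 6-month change does.

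**The detection comparison is a best case.** It sets proxies against the exact variable driving loss. In that same zero-change setting, a baseline-score test flags loss driven by change in only 10-37% of runs. More tests also bring chance findings: 18 comparisons with no selection gave at least one significant result in about 47% of runs (assumed inter-scale correlation 0.5, 150 enrolled, 30% loss). The added comparisons should therefore be read by effect size.

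**A stronger reading is tempting.** A reader might infer that the 6-month benefit will be overstated, or that the planned analyses are invalid. The documents do not support either. They do not show how many people will be lost or why, and one plausible pattern understates benefit.

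**Conclusion.** The gap is real and should be fixed. The planned analyses rest on people with the needed scores, no missing-data method is specified, and the drop-out check omits the variables most likely to reveal outcome-related loss. In an uncontrolled study aimed at 6 months or more, this leaves the main estimate open to bias in either direction.

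Confidence is high for the omission and low for its size. The figures illustrate what assumed loss rates, selection strengths and correlations of 0.6-0.8 would do to mean change in SD units. They are not forecasts for this study, and they do not translate directly into the effect size r that the SAP will report.

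**What to change.** Keep the Wilcoxon tests as primary and amend the SAP as follows.

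1. Extend the comparison of completers with drop-outs to baseline scores on all outcome scales and, for people lost by 6 months, to their 4-week scores and change. Interpret these by effect size rather than by p-values. Define 'completer' and report the number analysed at each visit.
2. Add, as a sensitivity analysis, a mixed model for repeated measures or multiple imputation using everyone with a baseline score. Report 4-week and 6-month contrasts with 95% confidence intervals for the continuous scales.

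**Cost.** SAP wording and modest extra analysis, with no new data or visits. Item 1 costs almost nothing. The model in item 2 has limits that should be stated. It assumes missing at random, gains less for people lost before 4 weeks, relies on approximate normality (the SAP expects otherwise for these outcomes), and only partly corrects loss driven by unseen 6-month outcomes.

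A scenario assuming no change in those lost is not advised as a substitute. With baseline-driven loss and correlation 0.7 it gives -0.220 × 0.8 = -0.176 to -0.150 × 0.6 = -0.090, further from -0.25 than the completers themselves.

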#### Intervention

The intervention will be administered in a group setting in which approximately 15-25 participants, unknown to each other, will meet for a one-time, 2-day, facilitator-led workshop. Each constellation will start with a brief interview between the facilitator and the active client to clarify the individual's goal with the intervention. This will be followed by a decision about which members/elements of the client's (inter)personal system will play a significant role in the issue presented, and these will be represented by other group members during the constellation.

The representatives (including the client's representative) will be positioned in the room by the client initially, with spatial distances, angles, and body postures meant to correspond to the client's inner image of the system ("problem constellation"). This will allow the facilitator to identify the dynamics beneath the client's presenting concern, while at the same time will help the client reflect on their internal experience from a more objective, partially external point of view (as they will be observers and not participants at this point). This part of the process will be largely non-verbal, focusing on what participants begin to experience as being part of the structure created by the active client (cf. Orban 2008).

Next, the representatives will be asked by the therapist about their physical sensations, feelings, and thoughts they will have while in their positions. Rearrangements, spatial adjustments, and brief, ritualized conversations will be made based on the principles of healthy functioning within a system until a constellation is identified that will offer a resolution or relief for the client (who at this point might become an active participant of the constellation if they feel ready to do so). Ideally, this "solution constellation" will provide a new, more adaptive framework for the client to feel, think, and behave in the given system (Hunger et al. 2015).

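### No planned test has a workshop term, so if changes correlate within workshops the p-values are too small, more so for therapist effects on change than for the Wilcoxon tests

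*Combined protocol and SAP*

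**What the plan says.** Under Participants and procedure, the protocol recruits people who intend to join a "2-day family constellation workshop on a fee-for-service basis (private setting) with one of the three professionals participating in the study". It describes no allocation to therapists, and it adds that "Participation in the study will be voluntary". Under Intervention, the treatment is "administered in a group setting in which approximately 15-25 participants, unknown to each other, will meet" once, over two days, and group members stand in for elements of each other's systems. The third aim in Background and aims is to report whether therapist effects are present.

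The SAP's primary rule is that "the effectiveness of the intervention will be investigated using Wilcoxon paired sample tests in the primary analyses", with separate comparisons from baseline to 4 weeks and to 6 months. The choice is justified by likely non-normality and the "occasionally ordinal nature (SCOFF) of the outcome variables". Secondary analyses follow: "repeated measures ANOVAs will be conducted as secondary analyses to investigate the main effect of time considering all three assessment points", and then "A further set of ANOVAs will be run to investigate therapist effects". The dependent variable of the therapist ANOVAs is not named.

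No analysis has a workshop factor, a random workshop effect or a clustered standard error. Therapist appears only in the last set of ANOVAs.

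**The concern.** People in the same workshop share a facilitator, a room and two days, and they take part in each other's constellations. Their changes may therefore resemble one another more than those of people from different workshops. A test that assumes independence then overstates the information in the sample.

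The therapist comparison is the most exposed planned use. Each workshop belongs to one therapist, so ordinary variation between workshops enters the therapist mean square, while the error term is variation between participants. A therapist difference could be declared when some workshops simply went better than others. For the Wilcoxon and time tests, the risk lies mainly with outcomes that change little.

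**Working it through.** **Inputs from the documents.** Three therapists; about 15-25 attendees per workshop; three assessments. There is no planned figure to reproduce, because ICC, alpha, sample size, number of workshops and number enrolled per workshop are not given.

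**Assumptions.** Nominal two-sided 5%; ICC of change scores from 0 to 0.10; m participants analysed per workshop; therapist ANOVA run on change. Because participation is voluntary and drop-out is expected, m may be well below 15-25, so values from 5 upwards are shown.

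**Formulas (large sample).**
- Design effect: DEFF = 1 + (m - 1) × ICC.
- Wilcoxon (1 df): true error = 2 × [1 - Φ(1.96/√DEFF)].
- Therapist F (2 numerator df): true error = exp(-2.996/DEFF).

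**One case in full (m = 10, ICC 0.05).** DEFF = 1 + 9 × 0.05 = 1.45. Wilcoxon: 1.96/√1.45 = 1.628, giving 10.4%. Therapist: exp(-2.996/1.45) = exp(-2.066) = 12.7%.

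| ICC | m | DEFF | Wilcoxon | Therapist ANOVA |
|---|---|---|---|---|
| 0 | any | 1.00 | 5.0% | 5.0% |
| 0.01 | 5 | 1.04 | 5.5% | 5.6% |
| 0.02 | 5 | 1.08 | 5.9% | 6.2% |
| 0.02 | 10 | 1.18 | 7.1% | 7.9% |
| 0.02 | 20 | 1.38 | 9.5% | 11.4% |
| 0.05 | 5 | 1.20 | 7.4% | 8.2% |
| 0.05 | 10 | 1.45 | 10.4% | 12.7% |
| 0.05 | 20 | 1.95 | 16.0% | 21.5% |
| 0.10 (extreme) | 25 | 3.40 | 28.8% | 41.4% |

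**Time ANOVA.** Take equal person-level error at the three assessments and unit variance of change, so e = (1 - ICC)/2. Let r be the correlation of workshop effects at the two follow-ups. Workshop variance on the two orthonormal time contrasts is v1 = ICC(1 + r)/3 and v2 = ICC(1 - r). With Dj = (m·vj + e)/((v1 + v2)/2 + e), true error = P[(D1·X1 + D2·X2)/2 > 2.996], where X1 and X2 are chi-square with 1 df. For m = 10, ICC 0.05 and r = 0.5: v1 = v2 = 0.025, e = 0.475, D1 = D2 = 0.725/0.5 = 1.45, error 12.7%. At r = 0.9 it is 10.7%, and at r = 0 it is 15.2%. The time test is thus inflated about as much as the therapist test, somewhat less or more depending on r.

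**Simulation under the null.** With 4 workshops per therapist, 6-14 analysed in each and ICC 0.05: Wilcoxon 9.8-11.2%, therapist ANOVA on change 12.9-14.4%, time ANOVA 11.2 / 13.8 / 16.2% at r = 0.9 / 0.5 / 0. If the therapist analysis is instead time × therapist (3 workshops per therapist, 20 analysed, ICC 0.05), its error is 26.2%, against 15.1% for the Wilcoxon.

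**Do workshop-level tests repair it?** With 2, 4 or 8 workshops per therapist and ICC 0-0.10, simulated error is 4.4-6.2% for the therapist F on workshop mean changes, 4.0-5.9% for signed ranks summed by workshop, and 4.2-5.6% for the multivariate time test on workshop means.

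**Do large changes survive?** With 4 workshops per therapist, about 10 analysed and ICC 0.05, a 0.5 SD change is significant in 99.7% of simulated studies with the ordinary Wilcoxon and in 98% with the workshop-level test. For 0.3 SD the figures are 86% and 68%.

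**The case against.** The strongest reply is that the harm is wholly assumed. The protocol even gives reasons for a small ICC: attendees do not know each other, they meet once, and each constellation serves one client's own goal. At ICC 0.01-0.02 with 5 analysed, the Wilcoxon error is only 5.5-5.9%. The study is also uncontrolled, so no p-value for pre-post change could establish effectiveness by itself, and the therapist ANOVAs are secondary. This stands as a limit on the size. It does not remove the omission, and the third aim depends directly on the affected test.

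A reader might infer that the primary Wilcoxon should be replaced. The documents do not support that: with ICC and number of workshops unknown, the power loss could be large for little gain. At ICC 0, about 5 analysed and 2 workshops per therapist, power for 0.3 SD falls from 34% to 25%.

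A reader might also want the therapist test adjusted for baseline. Participants sign up with a therapist, so clienteles may differ. Suppose they differ stably by 0.5 SD between the extreme therapists while change does not differ (10 analysed, ICC 0.05, retest correlation 0.5). The adjusted workshop-level test then rejected in 12.4% of simulated studies with 4 workshops per therapist and 21.7% with 8; a repeat run gave 10.9% and 20.9%. The unadjusted test stayed at about 4-6%.

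Nor does one therapist with a single workshop make the therapist test impossible. With 1, 4 and 4 workshops, or 1, 1 and 4, it kept its level (4.9% and 4.8%). Only one workshop for every therapist confounds the two fully.

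**Conclusion.** The point holds and should be fixed. That participants share workshops and that no test allows for it is plain from the text. That p-values are too small is conditional on positive within-workshop correlation of change. That the therapist test suffers more than the Wilcoxon also assumes it is run on change or as time × therapist; if run on score levels, the within-workshop correlation of levels matters instead.

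The inflation ranges from none at ICC 0, through a fraction of a percentage point at ICC 0.01 with 5 analysed, to roughly two to four times the nominal 5% at ICC 0.05 with 10-20 analysed. The 29% and 41% figures need both ICC 0.10 and 25 analysed per workshop, and should not be read as expected.

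A reader might infer that the effectiveness results would be biased or worthless. That does not follow. Mean change and the Reliable Change Index classification do not depend on the independence assumption, and a strong result can survive: a nominal p of 0.001 becomes about 0.02 at DEFF 1.95. The argument also concerns tests of change; it is not directed at the step in which "Baseline characteristics of study completers versus drop-outs will be compared".

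**What to change.** Store a workshop ID for each participant and report the number of workshops per therapist and the number analysed in each.

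1. **Therapist effects.** Name change from baseline as the dependent variable. Test therapist as a fixed factor, without baseline adjustment, against workshop-within-therapist variation, for example by an F test on workshop mean changes. Report therapist differences with 95% CIs and the workshop ICC. Show any baseline-adjusted version only as a sensitivity analysis. Only if every therapist runs a single workshop, state that therapist and workshop effects cannot be separated and make no therapist-effect claim.
2. **Effectiveness.** Keep the Wilcoxon tests. Beside them, prespecify a sensitivity analysis: drop zero changes, rank the absolute changes, restore the signs, sum by workshop (zeros count as 0, and a workshop with only zeros stays in), and apply a one-sample t-test with df = workshops - 1.
3. **Time.** Keep the repeated measures ANOVAs. Add a multivariate time test on workshop means (df 2 and workshops - 2), or a random workshop-by-time effect with small-sample degrees of freedom. A workshop intercept alone would cancel out of within-person time contrasts.

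Limit inference to these three therapists, and describe a change as robust only if it holds in both the planned and the workshop-level analysis.

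**Cost.** One stored variable and some SAP wording; the simple versions need only ranking, aggregation and standard tests. The price is fewer degrees of freedom, an imprecise ICC and lower power when workshops are few. For 0.3 SD at ICC 0 with about 10 analysed, power goes from 61% (Wilcoxon) to 44% (workshop-level) with 2 workshops per therapist, and from 89% to 83% with 4. Failure of the workshop-level test with few workshops is therefore weak evidence against a change.

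Therapist CIs widen too. With W workshops per therapist, the half-width is t(3(W - 1)) × √[2(ICC + (1 - ICC)/m)/W], against t × √[2/(W·m)] when workshops are ignored. At ICC 0.05 and m = 10, it goes from 0.63 to 1.21 SD with W = 2, from 0.44 to 0.61 with W = 4, and from 0.31 to 0.40 with W = 8.

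### The SAP leaves the therapist-effect ANOVAs unspecified: with non-random assignment, one permitted reading confounds therapist with case mix, and under any reading a non-significant F with eta squared cannot support absence

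*Combined protocol and SAP*

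**What the plan says.** - **Aim.** The protocol (Background and aims) lists as its third aim "providing information on the presence or absence of therapist effects".
- **Analysis.** The SAP says "A further set of ANOVAs will be run to investigate therapist effects". The effect size follows in the next sentence: "In these secondary analyses, effect size will be expressed by eta squared".
- **Neighbouring models.** Just before this, the SAP states that "repeated measures ANOVAs will be conducted as secondary analyses to investigate the main effect of time considering all three assessment points". Only the time effect is named there; therapist is not mentioned.
- **How clients reach a therapist.** Under Participants and procedure, participants attend "on a fee-for-service basis (private setting) with one of the three professionals participating in the study". No allocation procedure is described.
- **Providers.** The same section describes "one therapist with a background in clinical psychology, while the other two will be trained in medicine".
- **Baseline data.** A pre-intervention assessment is planned. The only baseline comparison in the SAP is completers against drop-outs; none is planned across therapists.
- **Not stated.** Sample size, numbers per therapist, power, an equivalence bound, and any confidence interval for the therapist comparison.

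**The concern.** A therapist effect, in the sense that matters for effectiveness, is a difference between therapists in how much their clients change. Assignment to therapist is not random and the providers differ in background, so the three clienteles may differ in severity before the workshop. The plan does not say which ANOVA will be run, and the candidates answer different questions. An ANOVA of follow-up scores, or the therapist main effect averaged over time points, compares how ill each clientele is. A therapist-by-time term, or an ANOVA of change scores, compares how much each clientele changed. Leaving this choice until the data are in means that the model can decide the answer to a stated aim.

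The second half of the aim, absence, is a separate problem. An F test and eta squared give no range of therapist differences that remain compatible with the data, so a non-significant result could reflect small groups as easily as similar therapists.

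**Working it through.** **No figure to reproduce.** The documents give no sample size, SD, correlation or power for this comparison. Everything below is an illustration under stated assumptions.

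**Step 1. False therapist effects under the confounded reading.**

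Assumptions: three equal groups of n = 40 (N = 120), within-therapist SD 1, pre-post correlation ρ = 0.7, the same true change under every therapist, and stable baseline means at −d/2, 0 and +d/2, where d is the gap between the outermost clienteles.

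The mean squared shift is (d²/2)/3 = d²/6, which is 0.0150 for d = 0.3 and 0.0417 for d = 0.5. The noncentrality of the F test is λ = N × (d²/6) / v, where v is the variance of the quantity analysed. The rejection rate at 5% follows from the noncentral F with 2 and 117 degrees of freedom.

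| Model | v | λ (d = 0.3 / 0.5) | Rejection (d = 0.3 / 0.5) |
|---|---|---|---|
| ANOVA of follow-up score | 1 | 1.80 / 5.00 | 20% / 49% |
| Therapist main effect (mean of baseline and one follow-up) | (1 + 0.7)/2 = 0.85 | 2.12 / 5.88 | 23% / 56% |
| Change score (same as therapist-by-time with two time points) | 2(1 − 0.7) = 0.6 | 0 / 0 | 5% / 5% |

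A simulation of the same setting (4,000 replicates) gave 7% / 12% for a baseline-adjusted ANCOVA: much lower than the unadjusted models, but above 5%, because one imperfectly reliable baseline does not fully remove a stable group difference.

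Sensitivity: with 25 to 60 clients per therapist the two unadjusted models range from 14% to 75%. A separate simulation with ρ = 0.6, three time points and d = 0.5 gave 25% to 85% for the unadjusted models at N = 60 to 198, and about 5% for therapist-by-time. With no baseline gap, every model stays near 5%.

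**Step 2. Does therapist-by-time always hold its level?**

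No. Suppose the baseline gap regresses, so that the follow-up gap is 0.7 times the baseline gap, with no therapist effect. For d = 0.5 the gap in change is 0.3 × 0.5 = 0.15 SD, and λ = 120 × (0.15²/6) / 0.6 = 0.75, giving 11% rejection at 40 per therapist. ANCOVA then stays at 5%. The ranking of the two corrections reverses.

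**Step 3. What a non-significant result can say about absence.**

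The 95% half-width for a pairwise difference in change is 1.96 × √(2(1 − ρ)) × √(2/n). With n = 35:
- ρ = 0.8: 1.96 × 0.632 × 0.239 = 0.30 SD
- ρ = 0.6: 1.96 × 0.894 × 0.239 = 0.42 SD

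Power to detect a real 0.3 SD range across three therapists (ρ = 0.6; lowest for a follow-up-only ANOVA, highest for ANCOVA) is 12–16% at N = 60, 17–25% at N = 100, 25–36% at N = 150 and 32–47% at N = 200.

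Eta squared does not fill the gap. With no therapist effect its expected value is (k − 1)/(N − 1) = 2/(N − 1), which is 2/59 = 0.034 at N = 60 and 2/99 = 0.020 at N = 100, and the plan attaches no interval to it.

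**The case against.** The strongest reply is that the SAP is silent, not wrong. A reader might infer that the planned ANOVAs leave out baseline and the therapist-by-time term. The documents do not support that. The sentence can mean the repeated measures models just described with therapist added, and such a factorial model would ordinarily carry the interaction. Change-score ANOVAs also fit. Under either, the case-mix problem does not arise in the form shown in Step 1. This stands, so the point is under-specification and not a demonstrated modelling error.

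Two further inferences also go beyond the text. A reader might take it that clients pick their therapist; the protocol says only that they attend "with one of the three professionals participating in the study", and date or location could decide. That assignment is not random is clear; active choice, and any actual difference in severity, is not stated. A reader might also infer that a null test will be reported as absence; the SAP contains no such rule, and the risk comes only from how the aim is worded.

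It is also fair that the rates depend on assumed gaps and group sizes, and that Step 2 shows neither correction is safe in general. The SAP itself recognises regression to the mean as a threat, though it deals with it only in the reliable-change analysis. Replacing eta squared with another index would be a matter of preference, and eta squared serves the SAP's stated wish for comparability with other studies; intervals can simply be added beside it.

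What the reply does not remove is that an SAP exists to settle this choice in advance, and that no reading of the sentence supplies an interval.

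**Conclusion.** The point holds as one of under-specification, and is a cheap improvement to a secondary analysis that carries a stated aim.

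- **Presence.** The wording permits models that confound therapist with case mix. If one were used, false therapist effects would appear in about 20% to 56% of studies, against about 5% for therapist-by-time. This rests on assumed inputs: 40 per therapist, correlation 0.7, a stable 0.3 to 0.5 SD baseline gap and identical change. If the clienteles do not differ at baseline, there is no excess.
- **Absence.** Under every reading, a non-significant F with eta squared cannot support absence. At an assumed 35 per therapist, differences in change of about 0.30 to 0.42 SD in either direction from the estimate would remain compatible with the data. The calculation treats participants as independent.

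The documents do not show that the wrong model will be used, that clients actively choose, or that a null will be called absence.

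**What to change.** Replace the single sentence in the SAP with text to this effect:

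1. Therapist effects will be tested as the therapist-by-time contrasts, that is, differences between therapists in change from baseline to 4 weeks and from baseline to 6 months. The therapist main effect will not be interpreted.
2. Baseline scores will be tabulated by therapist.
3. The three pairwise differences in change will be reported with 95% CIs, alongside eta squared.
4. A model of the follow-up score on therapist and baseline score will be given as a sensitivity analysis.
5. If the two models disagree, both will be reported and the therapist finding called inconclusive.
6. A non-significant result will be reported as not detected and judged by the width of the CI, not as absence.

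**Cost.** SAP wording and one extra model per outcome; all the variables are already collected. The real downside is that the two models can disagree when baseline differences regress to the mean, which item 5 addresses in advance.
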